### 16.2.1 NORMALIZATION PHASE

The normalization phase encompasses from Screening/Inclusion until complete normalization of serum TSH and T4 within the reference range for age is achieved and includes Visits 2 and 3. Subjects who at Visit 3 have not yet achieved TFTs normalization, based on the Investigator's judgement, will undergo one or more additional follow-up visits at appropriate time intervals (usually every two weeks) and dose adjustments until TFTs are normalized (e.g. Follow-Up Type 1, FU1). If the timing of FU1 visit overlaps with the next planned visit (V4-V8), it is possible to perform only the planned visit.

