### 16.2.3 VISIT 2 (STUDY DAY 8-15, i.e. 7-14 DAYS AFTER TREATMENT START)

During Visit 2 the PI or designee will complete the following via a TM visit, except for blood sampling:

- Verify concomitant medications;
- Record AEs;

- Assess the presence of signs and symptoms of hypo- or hyper- thyroidism (by parents' interview);
- Take blood samples for serum TSH, FT4 and, optional, TT4 (blood sampling is optional, at the discretion of the Investigator, for infants already on LT4);
- Perform dosing evaluation;
  - A different LT4 dose may be indicated and drug dispensed or shipped to parents/guardians if the dose must be adjusted;
- Record nutritional intake;
- Review eDiary completion (Treatment Compliance and CareCAT); and
  - If needed, further instructions will be provided to the parent/guardian on how to complete the eDiary and how to comply with the study requirements.

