### 19.3.2 EFFICACY OUTCOMES

The LT4 dose/kg will be calculated based on the daily LT4 dose used in the time period preceding the visit and the body weight measured during the visit. When dosing schedules alternating strengths over the course of the week are used, the daily dose will be calculated as the average daily dose on a weekly basis. The LT4 dose/kg required to maintain TSH in target range will be

analyzed at 12 months of age visit (V8) and when the subject is 2, 4, 6, 9, 15, 18 and 21 months of age (V4, V5, V6, V7, V9, V10, V11) by means of analysis of covariance, including treatment group, newly diagnosed neonates vs infants already on LT4 therapy, age at inclusion and center as covariate.

Laboratory parameters (TSH and FT4) will be analysed at each time point by means of analysis of covariance, including basal value, treatment group, newly diagnosed neonates vs infants already on LT4 therapy, age at inclusion and center as covariate. If an adequate number of observations will be reached, the same analysis will be repeated for the TT4 parameter; otherwise the TT4 results will only be summarised by descriptive statistics.

The events of TSH values above 4.5 mU/L will be analyzed with a logistic model for each study visit with treatment group, newly diagnosed neonates vs infants already on LT4 therapy, age at inclusion and center as covariates. The laboratory result with a TSH value above 4.5 mU/L reported for the visit will be considered the analysis event.

The events of FT4 values below the middle of the laboratory normal range will be analyzed with a logistic model for each study visit with treatment group, newly diagnosed neonates vs infants already on LT4 therapy, age at inclusion and center as covariates. The laboratory result with a FT4 value below the middle of the laboratory normal range reported for the visit will be considered the analysis event.

Parent satisfaction assessed by “Parents’ Satisfaction Questionnaire” at each in-clinic visits (and during visit V1 only for infants that are already in therapy) will be analyzed by means of analysis of covariance, including treatment group, newly diagnosed neonates vs infants already on LT4 therapy, age at inclusion and center as covariate.

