3.2 SAMPLE SIZE

Subjects were randomized in a 2:1 ratio to Treatment (Tirosint®-SOL) or Control (conventional therapy with LT4 crushed tablets). Considering a mean value of 6 mcg/kg/day of LT4 dose at 12 months of age and a standard deviation of 2 mcg/kg, a sample size of 102 neonates and infants (68 Treatment and 34 Control) will have 80% power to detect a difference of 20% in the LT4 dose between the groups using an independent t-test with a 0.050 two-tailed significance level. To account for a drop-out rate of maximum 20%, 126 neonates and infants will be enrolled in the study (84 Treatment and 42 Control) (Peroni 2013).

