6.1.2 Secondary efficacy variables

Laboratory parameters

- Thyroid Stimulating Hormone (TSH);
- Free Thyroxine (FT4);
- Number of events of TSH values above 4.5 mU/L;
- Number of events of FT4 values below the middle of the laboratory normal range

Frequency of dose adjustments

Percent number of subjects (%) who need a dose adjustment in the long-term follow up phase.

Parents' satisfaction questionnaire (PSQ)

The Parents' Satisfaction Questionnaire is completed by the parents/guardian in the eDiary:

at V1 only for infants who are already on TH therapy, and 0-3 days before in-clinic visits for all subjects.

Parents answer questions about the following topics:

- Coping and mental well-being;
- Drug preparation & administration;
- Treatment satisfaction; and
- Medication preference.

The PSQ score at each visit will be computed as sum of all questions scores assigned as reported in Appendix 3.

Caregiver administered Children's Acceptance Tool (CareCAT)

This questionnaire is completed within the eDiary during the first, the third and the eighth week of treatment.

Descriptors:

Swallows well – Medicine is swallowed down

- Observing the act of swallowing the medicine – '[I see that she] drinks the medicine and swallows'
- Ingesting the medicine in absence of negative behaviors – 'He swallows and does not give me a hard time'

Refusal – Resistance of the child (e.g. fighting, crying)

- Defensive behavior preventing the intake of medicine – 'By pushing the spoon' or 'fights with her hands' or 'turns away her head'
- Spitting up – Some medicine is coming out of the mouth immediately
- Forcing the medicine out actively – 'He spits or maybe blows the medicine out'
- Medicine passively leaving the mouth ('overflow' or 'spilling') – 'When the medicines runs down the mouth'

Vomiting – Within 30 minutes after swallowing the medicine the child brings up something [vomits]

- 'She takes out the medicine after feeling nauseous, then vomits it with food'

Medication not taken – No medicine went into the mouth of the child

- No oral intake of medicine – 'She does not want [to take the medicine] until the medicine did not get in [the mouth]'
- Intake without ingesting – 'I have tried to give her but [the medicine] was still not swallowed'

Growth assessments

The following variables about growth are collected: length (cm), weight (Kg) and head circumference (cm).

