9 STATISTICAL METHODOLOGY

9.1 GENERAL METHODOLOGY

Descriptive statistics

Categorical variables will be summarized by frequency (n) and percentages (%) and quantitative (continuous) variables using measures of central tendency (mean, median) and dispersion (minimum & maximum; 95% confidence intervals; values defining the limits of the 2nd and 3rd quartiles (25th percentile, 75th percentile); and the standard deviation.

P-values and Type I error

All p-value(s) will be rounded to three decimal places. Statistical significance will be declared if the rounded p-value is less than 0.050.

Two-sided 95% confidence intervals (CI) will be calculated.

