9.4.2 Secondary efficacy analyses

Laboratory parameters (TSH and FT4)

Laboratory parameters (TSH and FT4) will be analysed at each time point by means of analysis of covariance (mixed model), including basal value, treatment group, age at randomization and interactions between visit and treatment group as covariate.

Normal distribution for TSH and FT4 will be tested with Shapiro Wilks, if data result not to be distributed as a normal distribution a log transformation will be applied.

The mixed model will be adjusted with Kenward-Roger method and the unconstructed covariance matrix will be used as first choice (other matrixes will be considered if there will be convergence problems).

Summary descriptive statistics will be provided for each laboratory parameter. TSH and FT4 levels at each visit will also be compared between treatment groups by Wilcoxon Mann-Whitney test. This analysis will also be repeated stratified on neonates and infants.

Laboratory data will also be listed with clinically significant information.

TSH values above 4.5 mU/L

The events of TSH values above 4.5 mU/L will be compared between treatment groups at each visit and aggregate from Visit 2 to the last available visit using a Chi-squared test or, when the expected values in any of the cells of a contingency table are below 5 or the total number of observations is less than 20, Fisher exact test as appropriate.

FT4 values below the middle of the laboratory normal range

The events of FT4 values below the middle of the laboratory normal range will be compared between treatment groups at each visit and aggregate from Visit 2 to the last available visit using a Chi-squared test or, when the expected values in any of the cells of a contingency table are below 5 or the total number of observations is less than 20, Fisher exact test as appropriate.

Parent satisfaction assessed by “Parents’ Satisfaction Questionnaire”

Parent satisfaction assessed by “Parents’ Satisfaction Questionnaire” score at V3, V5, V6, V7, V8, V9, V10, V11 will be analyzed by means of analysis of covariance (mixed model), including treatment age at randomization and interactions between visit and treatment group as covariate.

Normal distribution for Parents’ Satisfaction Questionnaire score will be tested with Shapiro Wilks, if data results not be distributed as a normal distribution a log transformation will be applied.

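### The aggregate TSH and FT4 event tests do not state their unit; on the natural reading they pool repeated values from each child and test them as independent

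*SAP*

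**What the plan says.** SAP 6.1.2 lists among the secondary efficacy variables the "Number of events of TSH values above 4.5 mU/L", with a matching count for FT4 below mid-range. SAP 9.4.2 says that these events are "compared between treatment groups at each visit and aggregate from Visit 2 to the last available visit using a Chi-squared test", with Fisher's exact test instead if any expected cell count falls under 5 or there are fewer than 20 observations in all. No random effect, robust variance or other within-child term is given for either test. SAP 9.1 adds: "Statistical significance will be declared if the rounded p-value is less than 0.050".

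Protocol 19.3.2 planned per-visit logistic models for these endpoints and defined the event: "The laboratory result with a TSH value above 4.5 mU/L reported for the visit will be considered the analysis event". It has no aggregate test. The SAP version history shows the aggregate entering with Draft 1.1 (March 2026).

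Two features of the sampling schedule matter. At Visit 2, under protocol 16.2.3, "blood sampling is optional, at the discretion of the Investigator, for infants already on LT4". Under protocol 16.2.1 and 16.2.2, extra follow-up visits with blood draws are made until thyroid tests normalise, after a dose change, or, at the investigator's discretion, after an abnormal result. SAP 9.4.2 does not say whether results from those visits enter the aggregate.

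**The concern.** The child is the unit randomised. A chi-squared or Fisher test on a table of values assumes that each value is an independent observation, and repeated thyroid results in one child are unlikely to be. Switching from chi-squared to Fisher does not help, because Fisher's test makes the same assumption.

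The same SAP section uses a repeated-measures mixed model for continuous TSH and FT4, so the repeated structure is recognised there. It is dropped when the same results are dichotomised and pooled.

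With 31 children, a few with persistently high TSH who happen to fall in one arm could produce a nominally significant aggregate difference between formulations when none exists. The hormonal profile is one of the main objectives in SAP 3.1, and such a p-value would be read against the 0.050 threshold.

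**Working it through.** **Which unit does the text point to?**

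- SAP 6.1.2 names a number of events, where an event is a value.
- Protocol 19.3.2 defines an event as one laboratory result at a visit.
- For dose re-adjustment and for signs and symptoms, SAP 9.4.2 says explicitly that subjects are counted. For the TSH and FT4 events it does not.

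A programmer following the text would most likely pool values.

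**Inputs**

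- Level: 0.050 on the rounded p-value (SAP 9.1), two-sided (SAP 3.2 also uses a two-tailed 0.050 level).
- Children: 31 randomised (SAP 3), 2:1 allocation (SAP 3.3). Arm sizes are not given; 21 v 10 is assumed.
- Values per child, m: protocol Table 2 gives 6 or 7 scheduled visits from Visit 2 on, and one fewer where an infant's optional Visit 2 draw is skipped. So m is 5 to 7.
- Within-child correlation of the binary event, ρ: not in the documents. Assumed range 0.05 to 0.5.

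**The plan's own figure.** The documents give no operating characteristic for this test except the nominal 5%. Simulated with ρ = 0 and m = 6, the SAP's chi-squared/Fisher rule rejects in 4.7% to 5.5% of trials, so the nominal level is reproduced when values really are independent.

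**Formula.** Design effect DE = 1 + (m − 1)ρ, and true error = 2[1 − Φ(1.96/√DE)].

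Example with m = 6 and ρ = 0.3: DE = 1 + 5 × 0.3 = 2.5; 1.96/√2.5 = 1.24; true error = 21.5%. The 31 × 6 = 186 pooled values then carry about as much information as 186/2.5 ≈ 74 independent ones.

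| ρ | m = 5 | m = 6 | m = 7 |
|---|---|---|---|
| 0.05 | 7.4% | 8.0% | 8.6% |
| 0.1 | 9.8% | 11.0% | 12.1% |
| 0.2 | 14.4% | 16.6% | 18.6% |
| 0.3 | 18.6% | 21.5% | 24.2% |
| 0.5 | 25.8% | 29.5% | 32.7% |

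**Simulation check.** Beta-binomial data, 21 v 10 children, m = 6, no treatment effect, event rates 0.1 to 0.5, the SAP's switching rule, 20,000 runs per setting:

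| ρ | Rejection at nominal 5% |
|---|---|
| 0.05 | 7.2% to 8.2% |
| 0.1 | 10.3% to 11.2% |
| 0.2 | 15.6% to 17.2% |
| 0.3 | 20.6% to 22.3% |
| 0.5 | 29.7% to 31.0% |

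Giving 20% of the children a randomly shortened series changes little: about 11% at ρ = 0.1 and 30% at ρ = 0.5.

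**Child-level alternatives on the same model, m = 6**

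- Wilcoxon on per-child event counts (equivalent to proportions when every child has 6 values): 4.0% to 5.0% for ρ = 0.1 to 0.5, with 21 v 10 or 20 v 11 children. Other runs on the same model reached up to 6%.
- Chi-squared or Fisher on children with at least one event: 1.1% to 2.8%, which is conservative.

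**The case against.** The strongest objection is that the SAP never says values are pooled. The protocol's definition of an event was written for a per-visit model, so it reaches the aggregate only by inference. A table of children with any event is not excluded, and that table has no inflation. This stands: what the text establishes is an undefined unit. It does not remove the point, because the wording favours values and nothing says how 5 to 7 results would become one.

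A reader might infer that 11% to 31% is the true error rate of this plan. The documents do not support that, because they give no within-child correlation. At 0.05 the rate is only about 7% to 9%. The upper end is the least secure: dosing is reassessed at every visit to bring TSH back into range, and later visits are two to three months apart.

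A reader might also infer that Visit 2 values were selectively drawn in 27 of 31 children (31 less the 4 neonates in SAP 3.4). That number is only a ceiling. The protocol's document history shows that the draw was mandatory until Amendment 1 of 7 September 2023; first enrolment had been expected in September 2021, and screening closed on 31 March 2024. How many infants fell under the optional rule is not stated, nor is why any draw was made.

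Nor is it established that one abnormal episode will be counted several times. Follow-up visits are named separately from the numbered visits, and the SAP does not say that their results are included. The SAP only needs to settle this.

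Finally, these are secondary variables in an analysis declared exploratory throughout. The per-visit tests use one value per child, and the mixed models cover continuous TSH and FT4. All of that stands and limits the severity. But an exploratory p-value held to a 0.050 threshold should still be valid for its data.

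**Conclusion.** The point holds conditionally and should be fixed. The unit of the aggregate TSH and FT4 event tests is not defined. On the natural reading they ignore within-child correlation, and any positive correlation makes them anti-conservative. The size is about 7% to 33% true error against a nominal 5%, for assumed correlation 0.05 to 0.5 and 5 to 7 values per child, or about 11% to 31% for 0.1 to 0.5 at 6 values. The 21:10 split is also assumed. If the table counts children with any event, there is no inflation.

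The consequence is two potentially misleading aggregate p-values. No confirmatory claim fails, and the rest of the hormonal analysis is untouched.

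**What to change.** In SAP 9.4.2:

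1. State that the child is the unit of the aggregate comparison. For each child, compute the proportion of available scheduled-visit values with an event, separately for TSH and FT4, and compare arms by Wilcoxon. A logistic GEE clustered on child with a small-sample correction is an alternative; its error rate was not simulated here. Event totals can remain as descriptive statistics.
2. Restrict numerator and denominator to scheduled visits. Leave out follow-up and unscheduled results, since those draws can be prompted by abnormal results or dose changes and could count one episode several times.
3. Repeat the aggregate without Visit 2 as a sensitivity analysis, because that draw became optional for infants already on LT4 under Amendment 1. Visit 2 can stay in the main aggregate.

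The cost is a few sentences and minor programming, with no new data. The p-value will usually be less extreme than that of a pooled test.

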		
 
• In Section 15 Study Assessments and Procedures it has been clarified when clinically significant abnormalities detected at study assessments are to be recorded as medical history or AEs and when not.
 
• Section 15.1.2 Parents' Satisfaction Questionnaire has been updated to ask Investigators to verify completion of the questionnaire and, if not completed, ask parents to complete it on site during the visits, in order to improve compliance with this assessment.
 
• Section 16.1 Screening/Inclusion (Randomization) – Visit 1 (Day -14 to 1) and Table 1 Schedule of Evaluations: the definition of “first day of study drug administration” for subjects who were already on tablets and remain on tablets during the study has been clarified.
 
• Sections 16.2.1 Normalization Phase, 16.2.2 Long-Term Follow-Up Phase and Table 1 Schedule of Evaluations: it has been clarified that if a Follow-Up Visit (Type 1 or 2) overlaps with a planned visit, it is possible to perform only the planned visit, consistently with SOC.
 
• Section 16.2.2 and Table 1 Schedule of Evaluations: Follow-up Type 2 visits have been made optional, at Investigator's judgement, in case an abnormal T4 or TSH are found, for consistency with the SOC (they remain mandatory in case of dose adjustment).
 
• Sections 7.2 Organizational and Administrative Structure and 17.5 Reporting and 17.7 Follow-up: a new email address of Drug Safety Unit for SAEs notification has been added, the list of persons to be informed has been updated, and some instructions regarding the information to be provided by the Investigator have been added.
 
• Section 18.1 Data Collection: the latest definition of ALCOA has been added.
 
• Sections 7 Protocol Synopsis and 19.3.2 Efficacy Outcomes: statistical analysis of TT4 will be conducted only if an adequate number of observations will be available, since the evaluation of this laboratory parameter at each visit will be optional. Moreover, the statistical analysis for events of TSH values above 4.5 mIU/L and FT4 values below the middle of the laboratory normal range has been modified from analysis
 

--	--	--

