## 7.1 SCHEDULE OF EVALUATIONS (SOE)

**Table 1 Schedule of Evaluations**

Visit	V1	Treatment start	V2	V3	FU1 a	V4	V5	V6	V7	V8	V9	V10	V11	FU2 b
Age at Visit	Varies		Varies	Varies		2 months (60 days $\pm 7$ )	4 months (120 days $\pm 14$ )	6 months (180 days $\pm 14$ )	9 months (270 days $\pm 14$ )	12 months (365 days $\pm 21$ )	15 months (455 days $\pm 21$ )	18 months (545 days $\pm 21$ )	21 months (635 days $\pm 21$ )	
Study Day	-14/1 c	1	8-15 d	22-29 d		Varies d	Varies d	Varies d	Varies d	Varies d	Varies d	Varies d	Varies d	
Phase			TFTs normalization phase			Long-term follow-up phase								
Visit Type	Clinic		TM	Clinic	TM	TM	Clinic	Clinic	Clinic	Clinic	Clinic	Clinic	Clinic	TM
Informed Consent	X													
Demographics	X													
Medical History	X													
Concomitant Medications	X		X	X	X	X	X	X	X	X	X	X	X	X
Eligibility	X													
Adverse Events	X		X	X	X	X	X	X	X	X	X	X	X	X
Randomization	X c													
Physical Exam e	X			X			X	X	X	X	X	X	X	
Signs and symptoms of hypo- and hyper-thyroidism	X		X	X	X	X	X	X	X	X	X	X	X	X
Body Measurements f	X			X			X	X	X	X	X	X	X	
Nutritional Intake	X		X	X	X	X	X	X	X	X	X	X	X	X

a Subjects who at V3 have not yet achieved TFTs normalization will undergo one or more additional follow-up visits at appropriate time intervals (usually every 2 weeks) until TFTs are normalized (e.g. Follow-Up Type 1, FU1). If the timing of FU1 visit overlaps with the next planned visit (V4-V8), it is possible to perform only the planned visit.

b After V4, if a dose adjustment is needed or, at Investigator's judgement, if an abnormal T4 or TSH are found, additional follow-up visit(s) (2-6 week intervals) should be performed until normalization occurs (e.g. Follow-Up Type 2, FU2). If the timing of FU2 visit overlaps with the next planned visit (V5-V11), it is possible to perform only the planned visit.

c The procedures of screening and inclusion at V1 may be spread over multiple days (particularly when laboratory results need to be collected), but should be completed within 2 weeks with Randomization on Day 0 or 1. Day 1 is the first day of study drug administration (for subjects continuing on tablets, the first day of drug administration within the study).

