### 16.2.2 LONG-TERM FOLLOW-UP PHASE

The long-term follow-up phase begins once TFTs normalization has been achieved and includes Visits 4 to 11.

If a change in LT4 dose is needed or, at the discretion of the Investigator, if an abnormal T4 or TSH are found, an additional follow-up visit should be performed 2-6 weeks after the dose change or abnormal finding (e.g. Follow-Up Type 2, FU2). If the timing of FU2 visit overlaps with the next planned visit (V5-V11), it is possible to perform only the planned visit.

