#### **16.2.14 FOLLOW-UP TYPE 2 (FU2):**

During FU2 the PI or designee will complete the following via a TM visit, except for blood sampling:

- Verify concomitant medications;
- Record AEs;
- Assess the presence of signs and symptoms of hypo- or hyper- thyroidism (by parents' interview);
- Take blood samples for serum TSH, FT4 and, optional, TT4;
- Perform dosing evaluation;
  - A different LT4 dose may be indicated and drug dispensed or shipped to parents/guardians if the dose must be adjusted;
- Record nutritional intake;
- Review eDiary completion (Treatment Compliance);
  - Report and resolve discrepancies that are noted in treatment compliance; and
  - If needed, further instructions will be provided to the parent/guardian on how to complete the eDiary and how to comply with the study requirements.

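### The aggregate TSH and FT4 event comparisons do not say whether triggered follow-up samples count or whether the unit is the child or the sample; pooled by sample, they would partly measure how often a child was re-sampled

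*SAP*

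**What the plan says.** **The endpoint and the window.** SAP 6.1.2 words the TSH endpoint as "Number of events of TSH values above 4.5 mU/L" and the FT4 endpoint in the same way, so both count values. SAP 9.4.2 tests each of them per visit and then "aggregate from Visit 2 to the last available visit using a Chi-squared test", with Fisher's exact test when cells are small. It gives no rule for several values from one child and does not mention follow-up or unscheduled results. The aggregate comparison entered the SAP with draft 1.1 (09/03/2026).

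**The protocol's event rule.** Protocol 19.3.2 has a rule for a logistic model fitted visit by visit: "The laboratory result with a TSH value above 4.5 mU/L reported for the visit will be considered the analysis event". The SAP does not use that model and does not restate the rule for the aggregate.

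**Which samples exist.** Besides the numbered visits there are three other sources of TSH and FT4 values:

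- FU1: children judged not normalised at V3 "will undergo one or more additional follow-up visits at appropriate time intervals", usually every two weeks until normal (Protocol 16.2.1).
- FU2: expected after a needed dose change and, "at the discretion of the Investigator, if an abnormal T4 or TSH are found, an additional follow-up visit should be performed" (Protocol 16.2.2). The FU2 procedures include "Take blood samples for serum TSH, FT4 and, optional, TT4" (Protocol 16.2.14).
- Unscheduled visits: results are recorded if blood is drawn (Protocol 16.2.16).

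The Visit 2 draw is itself optional for infants already on LT4 (Protocol 16.2.3). All staff know the allocation (SAP 3.3).

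**The concern.** A scheduled sample is taken because of the calendar. An FU1 or FU2 sample is taken because something happened: tests were not normal at V3, the dose was changed, or a value was abnormal and the investigator chose to repeat it. If both kinds are pooled and each value counts as one observation, a child with one abnormal result contributes extra samples at a time when the next result is more likely than usual to be abnormal. Both the event count and the proportion then depend on re-sampling practice. Two arms with identical control at scheduled visits could show different event rates if one arm was re-sampled more often, and in an open-label trial nothing prevents that.

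The aggregate also matters because it is the only event comparison not split into per-visit tables, which are very small with 31 children. As written, two programmers could each follow the SAP and obtain different results.

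**Working it through.** The documents give no event rate, re-sampling frequency or planning figure for these comparisons, so there is no stated figure to reproduce. Every event and re-sampling input below is an assumption.

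**1. Wording side by side.** Where the SAP wants numbered visits it tends to list them: LT4 dose at V4–V11 (9.4.1), the questionnaire at V3 and V5–V11, and dose re-adjustment from Visit 4 to Visit 11 (9.4.2). Protocol 19.3.4 ties signs and symptoms to planned visits. The aggregate event window has an open end and no such limit. Protocol Table 1 puts FU1 and FU2 in its visit row. The text therefore admits these samples without saying that they are included.

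**2. Effect on the pooled rate.** Assume 6 scheduled samples per child, a true event probability of 0.22 in both arms, and repeats until normal with a maximum of 4, each repeat abnormal with probability 0.5. Scheduled events per child are 6 × 0.22 = 1.32. A followed event yields 1 + 0.5 + 0.25 + 0.125 = 1.875 repeat draws on average, of which 0.5 × 1.875 = 0.9375 are events.

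| Events followed up | Samples per child | Events per child | Pooled rate |
|---|---|---|---|
| 100% | 6 + 1.32 × 1.875 = 8.475 | 1.32 + 1.32 × 0.9375 = 2.56 | 30% |
| 50% | 6 + 0.66 × 1.875 = 7.238 | 1.32 + 0.66 × 0.9375 = 1.94 | 27% |
| 0% | 6 | 1.32 | 22% |

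Re-sampling after 100% v 50% of events thus gives 30% v 27%, with no true difference.

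**3. Sensitivity to the repeat probability.** With no cap on repeats, K scheduled draws, event probability p, follow-up probability r and repeat event probability q, the follow-up draws are f = Kpr/(1 − qr) and the pooled rate is (Kp + fq)/(K + f). For K = 6, p = 0.20, r = 1:

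- q = 0.2: f = 1.2/0.8 = 1.5; rate 1.5/7.5 = 20%, but the count rises from 1.2 to 1.5 per child.
- q = 0.3: f = 1.2/0.7 = 1.714; rate 1.714/7.714 = 22%.
- q = 0.5: f = 1.2/0.5 = 2.4; rate 2.4/8.4 = 29%.
- q = 0.7: f = 1.2/0.3 = 4.0; rate 4.0/10.0 = 40%.

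The rate moves only if repeats have a different event probability from scheduled draws. If they are events less often, for example after a low TSH, it falls.

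**4. False-positive rate of the SAP's test.** Simulation with 2,500 runs per scenario: 21 v 10 children (2:1 assumed, because the split of the 31 is not given), a true 25% rate in both arms, 6 scheduled draws, at most 4 repeats per event, nominal 5% level. Results from one child are either independent or correlated (between-child SD 1 on the logit scale).

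| Data and unit | Re-sampling by arm | q | Observed rates | Rejects, independent | Rejects, correlated |
|---|---|---|---|---|---|
| All samples pooled | 50% v 50% | 0.5 | 28% v 28% | 8% | 17% |
| All samples pooled | 50% v 50% | 0.7 | 32% v 32% | 12% | 21% |
| All samples pooled | 90% v 30% | 0.5 | 32% v 27% | 14% | 22% |
| All samples pooled | 90% v 30% | 0.7 | 40% v 29% | 40% | 43% |
| Scheduled samples pooled | any | – | 25% v 25% | 4.4–5.6% | 13–14% |
| Children with ≥1 scheduled event | any | – | – | 1.6–2.5% | 1.6–3.0% |

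Dropping follow-up draws removes the re-sampling bias but not the effect of correlated values from one child. Counting children deals with both, and is conservative at this size.

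**5. Ever/never.** A repeat triggered by an event adds nothing to an ever/never count, because the child is already counted. Follow-up triggered otherwise, such as by a dose change, can add a little. Let π be a child's event probability (mean 0.22, logit SD 1) and g the chance that a non-event visit leads to one extra draw. Then P(ever) = 1 − E[{(1 − π)(1 − gπ)}⁶]. This gives 66% for g = 0, 70% for g = 0.15 and 73% for g = 0.30.

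**The case against.** The strongest reply is that the sponsor meant V2 to each child's last numbered visit. End of study falls anywhere from V8 to V11 by age at inclusion (Protocol Table 2), which would explain the wording. The same sentence also has a per-visit comparison, the protocol counts the result reported for the visit, and SAP 4.1 mentions unscheduled values explicitly when it wants them for baseline. This reading is possible. It means that inclusion of follow-up samples cannot be stated as fact, but it does not settle the matter, because the SAP never says so and the protocol's rule belongs to a model the SAP does not use.

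Some stronger inferences are tempting and should not be drawn:

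- *All follow-up sampling is at the investigator's discretion.* FU2 after a dose change is not optional, although the dose decision is the investigator's. Discretion covers FU2 after an abnormal value and the judgement of non-normalisation at V3.
- *The solution arm was re-sampled more because only its infants change product.* The documents give no re-sampling counts. Control children may also change LT4 source (Protocol 13.1.1), and V3 can serve as the repeat test after a switch.
- *Amendment 1 created a difference by relaxing FU2 after abnormal values.* It applied to both arms.
- *An ever/never measure carries the same bias.* It does not; see step 5.
- *The bias raises event rates.* Follow-up after a low TSH could lower the TSH rate. An FT4 value below mid-range may be normal and trigger nothing.

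It also stands that the illustrative inputs are invented and that equal re-sampling creates no expected difference in rates between arms.

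**Conclusion.** The point holds as a gap in specification with a real consequence. SAP 9.4.2 leaves open which samples enter the aggregate and what the unit is. One permissible reading pools samples whose existence depends on earlier results or on dose changes in an open-label trial. On that reading the event rates and counts are partly a measure of re-sampling. The size and direction cannot be known from the documents. Under the stated assumptions the distortion runs from none (no re-sampling), through 30% v 27% from a common 22%, to 40% v 29% from a common 25% in a harsher case. The pooled test rejects in 14–43% of null runs when re-sampling is 90% v 30%.

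A reader might infer that the planned comparison is certainly biased, or biased for or against Tirosint-SOL; the documents support neither. The comparison is secondary and all efficacy analyses are declared exploratory in 31 children. It is worth correcting, at modest priority.

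**What to change.** In SAP 9.4.2, for both aggregate event analyses:

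1. Limit the data to one result per child per protocol-scheduled visit from V2 onward in that child's row of Protocol Table 2. Where a planned visit was performed in place of an FU1 or FU2 visit, count it as the planned visit. Exclude other FU1, FU2 and unscheduled results.
2. Replace the chi-squared test on pooled values by a comparison of children with at least one event, or by a repeated-measures model for the binary result.
3. Report the number of FU1, FU2, unscheduled and optional V2 draws per child by arm, and show the follow-up and unscheduled results descriptively. The V2 draw lies inside the window on any reading, and is optional for infants already on LT4, about 27 of the 31 children (31 less the 4 neonates in SAP 3.4).

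The cost is a few sentences and a programming filter, with no new data. The downside is that excursions seen only at follow-up visits appear descriptively and not in the comparison. If V2–V11 was always intended, step 1 only writes that down.
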